Alloclassic® Variall® Cup Ceramic Bearing System in Total Hip Arthroplasty

A multi-center, prospective, non-controlled post market surveillance study

PROTOCOL No. CME2014-03H

NCT NUMBER: NCT03672370

PROTOCOL VERSION:
2014-09 - REV. 01

STUDY SPONSOR

**ZIMMER GMBH
[name]
[name]
SWITZERLAND**

Title:	Alloclassic® Variall® Ceramic Bearing System in Total Hip Arthroplasty A multicenter, prospective, non-controlled post market surveillance study
Sponsor:	Zimmer GmbH
Objectives:	
The objectives of this study are to obtain survival and outcomes data on the Alloclassic® Variall® Cup in combination with the BIOLOX® delta Taper Liner when used in primary total hip arthroplasty. This will be done by analysis of standard scoring systems, radiographs and adverse event records. Data will be used to monitor pain, function and survivorship, and to confirm the safety and performance of the Alloclassic® Variall® Cup. Evaluation of squeaking and ceramic fracture rate will be an additional objective.
 
Safety will be evaluated by monitoring the frequency and incidence of adverse events.
 
Performance will be based on the implant survival, the overall pain and functional performances, subject quality-of-life and radiographic parameters of study subjects who received the Alloclassic® Variall® Cup. Pain and functional performance will be measured using the Harris Hip Score, survivorship will be based on removal or intended removal of the device. Subject quality-of-life will be determined by evaluation of the EQ-5D and the Oxford Hip Score, and radiographic parameters by analysis of x-rays.

Indication/ Target Population:	Patients, suffering from severe hip pain and disability requiring total hip arthroplasty, who meet the inclusion/ exclusion criteria.
Study Design:	Multicenter, prospective, non-controlled
Clinical Phase:	Post-market
Number of Subjects:	A total of 100 patients will be enrolled in this study
Length of Study:	12 years (2 year enrollment plus 10 years follow-up): follow-up visits at 3 months, 1, 2, 3, 5, 7, and 10 years post-operatively.
Study Device:	
Alloclassic® Variall® Cup in combination with:
 
Ceramic-on-Ceramic Articulation: BIOLOX® delta Taper Liner and BIOLOX® delta Femoral Head
 
Femoral Component: Avenir® uncemented Stem or Alloclassic® Variall® Stem

Comparator Device/ Procedure:	None
Clinical Assessments:	Evaluations will be made using the Harris Hip Score, Oxford Hip Score, EQ-5D and radiographic evaluation.
Safety Assessments:	Safety will be assessed by appropriate recording and reporting of adverse events throughout the study. All system components are CE marked and commercially available
Statistical analysis:	Data collected will be summarized and reported to each participating Investigator. Statistical analysis is conducted by Zimmer or its designee.

General Statistical Method:

The assessment of efficacy for subjects receiving the total hip replacement system will be determined using the overall pain score and functional performance. Clinical success will be defined as a modified Harris Hip score of > 80 that included a rating of 'mild', or 'no pain'; a failure will be defined as a modified Harris Hip score < 80. Any study hip that required a subsequent surgical intervention where a stem head, cup, or liner was removed, or where a removal was planned, was considered a failure regardless of the Harris Hip score. Success rates will be expressed as percentages and primary summary results will be presented in tables which will contain the number and percentage of patients classified as a clinical success for the treatment group.

The assessment of safety will be evaluated by monitoring the frequency and incidence of adverse device effects in investigational subjects. As part of the safety profile, a survival analysis will be done.

Additionally, there are measures of interest which will be used to assess the investigational device such as radiographic success, all components included in the assessment of radiologic success, the EQ-5D, Oxford Hip Score, concomitant medication usage, and incidence of adverse events.

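### Does leaving *the device* undefined by component make the survivorship endpoint unusable?

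*Combined protocol and SAP*

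**What the plan says.** All the relevant text is in the synopsis of the combined protocol and SAP.

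- **Objectives, event:** "survivorship will be based on removal or intended removal of the device". No components are listed.
- **Objectives, opening aim:** the study is to obtain "survival and outcomes data on the Alloclassic® Variall® Cup in combination with" the ceramic liner.
- **Objectives, confirmatory aim:** the data are to "confirm the safety and performance of the Alloclassic® Variall® Cup". Liner, head and stem are not named here.
- **Objectives, performance:** "Performance will be based on the implant survival", followed by pain, function, quality of life and radiographs. The same section adds: "Evaluation of squeaking and ceramic fracture rate will be an additional objective".
- **Study Device row:** the cup combined with the ceramic liner, the ceramic femoral head and a stem, given as "Avenir® uncemented Stem or Alloclassic® Variall® Stem".
- **General Statistical Method, survival:** "As part of the safety profile, a survival analysis will be done". No event is named.
- **General Statistical Method, clinical failure:** a study hip fails, whatever its Harris Hip Score, after a "subsequent surgical intervention where a stem head, cup, or liner was removed, or where a removal was planned".

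**The concern.** The event clause rests on a noun that it does not define, and nearby text suggests more than one scope. If *the device* is everything in the Study Device row, a stem or head removal that leaves cup and liner in place counts as loss of survival, which is wider than the opening aim. If it is the cup alone, a liner exchange with the cup retained is not an event, which is narrower than that aim. Only a cup-plus-liner reading matches the aim exactly, and no sentence selects it.

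Implant survival is the first-named performance measure, and the unsettled cases include liner and head removals, which could follow the ceramic fractures that the study sets out to count. Two analysts could report different survival figures from the same records. Because follow-up lasts 10 years, the scope could in principle be chosen after the removals are known.

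**Working it through.** **1. What each scope counts.** The supplied text supports three scopes for *the device*. The last column shows the separate clinical failure rule.

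| Removed | Cup only | Cup + liner | Study Device row | Clinical failure |
|---|---|---|---|---|
| Cup | event | event | event | failure |
| Liner only | no | event | event | failure |
| Head only | no | no | event | failure |
| Stem with head | no | no | event | failure |
| Stem, head retained | no | no | event | depends on how *stem head* is read |

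**2. Weight of each scope.** The Study Device row is the only labelled statement of what the device is, and it stands in the same synopsis as the event clause. The General Statistical Method fits that reading: it refers to the whole hip replacement system, and its failure rule pairs actual with planned removal across several components, as the event clause pairs actual with intended removal. The cup-only scope is inferred by joining two sentences, neither of which defines the device. It also sits badly with the opening aim, which attaches survival to the cup with its liner.

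**3. Size of the ambiguity.** The plan states no survival figure to reproduce. Its only relevant input is the enrolment of 100 patients. Assume one hip per patient and no censoring. Let *b* be cup removals, which count under every scope, and *d* the removals that count only under a wider one. The documents give no revision rate, so both are assumed.

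- Narrow scope: S = 1 − b/100
- Wide scope: S = 1 − (b + d)/100
- Difference: d/100, which is 1 percentage point per disputed removal

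The exact (Clopper-Pearson) 95% limits for x events in 100 are the 2.5% point of Beta(100 − x, x + 1) and the 97.5% point of Beta(101 − x, x). For x = 0 the upper limit is 100%.

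| b | Narrow estimate (95% CI) | Wide estimate at d = 5 (95% CI) |
|---|---|---|
| 0 | 100% (96.4 to 100) | 95% (88.7 to 98.4) |
| 2 | 98% (93.0 to 99.8) | 93% (86.1 to 97.1) |
| 4 | 96% (90.1 to 98.9) | 91% (83.6 to 95.8) |

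With b = 4, five disputed removals leave the wide estimate inside the narrow interval. With b = 2, five bring it to the lower limit. With b = 0, up to three stay inside (97% against 96.4%), and four or five do not.

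**4. Direction.** Every event under a narrower scope is also an event under the Study Device row. With complete follow-up, the natural reading therefore gives the lowest survival figure of the three.

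**5. What depends on it.** The supplied text has no survival target, comparator or test. The main results tables report clinical success, where a cup, liner or head removal is a failure under either reading of *stem head*. Ceramic fracture is evaluated as an objective of its own, and adverse events are recorded throughout. A fracture that leads to a liner or head exchange is therefore visible whichever survival scope is used.

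**The case for a change.** The strongest reply is that a natural referent is not a stated one. Nothing links the event clause to the Study Device row, and adopting the row makes the event wider than the survival named in the opening aim without saying that this is intended. The sampling interval is also no defence: the scopes are applied to the same patients, so the gap between them is a difference in what is estimated, not chance. Finally, an open scope over 10 years leaves room for a convenient choice.

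Part of this stands. The scope is not written down, and a reader who wants cup and liner survival alone would need it reported separately. The intervals show scale only. But wider than the aim is not the same as wrong. The cup and liner are studied as part of a total hip replacement, and survival of the construct is a coherent measure of that. The room for a convenient choice is limited by a labelled default that is also the least flattering scope. Moreover, the clinical failure rule cannot be applied without knowing which component was removed, so cup and liner removals can be separated at analysis.

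The phrase *stem head* is a smaller matter. It may mean the head alone, or a comma may have been lost when the text was extracted. It affects only a stem removed with its head retained.

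**Conclusion.** The concern is accurate on the wording but does not call for a change. The component scope of survivorship is unstated in the supplied text, which is mainly a synopsis, so a fuller definition may exist elsewhere. An analyst working from this text would take the Study Device row as the device, count removal or intended removal of any listed component, and obtain a valid survival figure for the construct. No stated rule leads to a wrong result.

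The most that is at stake is 1 percentage point of crude survival per disputed removal, assuming 100 single hips without censoring. That is up to 5 points across the assumed range of 0 to 5. In a single-arm surveillance study with no survival threshold, this alters a descriptive figure and no stated decision. The conclusion would be different if survival were tested against a target or comparator, neither of which the supplied text contains.

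### The synopsis promises to confirm safety and performance, but the planned output (counts, percentages and an unspecified survival analysis) supports estimation only

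*Combined protocol and SAP*

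**What the plan says.** All references are to the synopsis of the combined protocol and SAP.

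- **Title and design.** The study is "multi-center, prospective, non-controlled", described as post-market surveillance. The comparator row says there is none.
- **Objectives.** The first aim is to collect survival and outcome data. The data are then to be used for monitoring pain, function and survivorship, and "to confirm the safety and performance of the Alloclassic® Variall® Cup". Squeaking and ceramic fracture rates are an additional objective.
- **Number of Subjects.** "A total of 100 patients will be enrolled in this study". No reason for the number and no precision target are given.
- **Length of Study.** Seven follow-up visits run from 3 months to 10 years. None is named as the visit at which success is judged.
- **General Statistical Method, efficacy.** A patient is a clinical success with a modified Harris Hip score above 80 and mild or no pain. A hip with a component removed, or with removal planned, "was considered a failure regardless of the Harris Hip score". At study level, "Success rates will be expressed as percentages and primary summary results will be presented in tables", and the tables hold a count and a percentage.
- **General Statistical Method, safety.** Safety rests on "monitoring the frequency and incidence of adverse device effects in investigational subjects", and "As part of the safety profile, a survival analysis will be done". No estimator, time point, interval or target survival is given.

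**The concern.** To confirm something, there must be a standard to confirm it against. Without a control group, that standard can only be an external reference value judged with its uncertainty. The plan names no reference value and no measure of uncertainty. The Harris Hip threshold classifies a patient; it does not say what proportion of successes would show that the cup performs as it should.

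The final report could therefore state that performance is confirmed on the strength of a percentage alone. The benchmark and the visit could be chosen after the results are known. With 100 patients at most, and probably fewer at 10 years, the uncertainty around a favourable percentage is large enough to matter. The fracture objective is the clearest case, because a reported 0% looks conclusive and is not.

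**Working it through.** **Plan's own figure.** The sample size of 100 cannot be reproduced. The documents give no alpha, power, expected rate, reference rate, margin, precision target or dropout. What can be checked is how much uncertainty 100 patients leave.

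**Inputs.** From the documents: n = 100, one group. Assumed for illustration: the observed counts, 70 evaluable patients at a late visit, a 90% reference rate, and true rates of 95% and 97%.

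**Step 1: intervals for a proportion.** The exact (Clopper-Pearson) 95% limits for x successes in n are

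- lower = 2.5th percentile of Beta(x, n − x + 1)
- upper = 97.5th percentile of Beta(x + 1, n − x)

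| Observed | Rate | Exact 95% interval |
|---|---|---|
| 90/100 | 90% | 82.4% to 95.1% |
| 95/100 | 95% | 88.7% to 98.4% |
| 63/70 (70 assumed) | 90% | 80.5% to 95.9% |

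Read as implant survival, 95/100 treats every patient as followed to the time point. Censoring over 10 years would widen that interval.

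**Step 2: zero ceramic fractures.** With x = 0 the two-sided 95% upper limit is 1 − 0.025^(1/n). For n = 100 this is 1 − 0.025^0.01 = 0.0362, or 3.6%. The chance of seeing at least one fracture is 1 − (1 − p)^100. That is 39.4% if the true rate is 0.5% and 63.4% if it is 1%, so a study with no fractures would be unsurprising at either rate.

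**Step 3: what a confirmation rule would require.** Suppose the rule were that the lower exact 95% limit must exceed 90% (assumed reference).

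- At n = 100: 95/100 has a lower limit of 88.7% and fails; 96/100 has 90.07% and passes. The requirement is at least 96. P(X ≥ 96) is 43.6% if the true rate is 95% and 81.8% if it is 97%.
- At n = 70 (assumed): at least 68 are needed (lower limit 90.06%). P(X ≥ 68) is 31% at a true rate of 95% and 65% at 97%.

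Other goals give different answers at n = 100. A goal of 80% with a true rate of 90% needs at least 89 successes and has 70.3% power. A goal of 85% with a true rate of 95% needs at least 93 and has 87.2%. The same 85% goal with a true rate of 90% has 20.6%. Whether 100 patients can confirm anything depends on a goal that the plan does not state.

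**The case against.** The strongest reply is that this is a descriptive post-market study of CE-marked components. Its objectives open with data collection and monitoring, *confirm* is one verb in one clause, and such a study needs neither a hypothesis test nor a power calculation. That is right, and it limits the point: the fault lies in the mismatch between the verb and the output, and the choice of 100 patients is not itself an error.

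Three further replies carry some weight.

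- **A criterion and a survival analysis do exist.** True. But the criterion works at patient level only, and the survival analysis has no method, interval, time point or target.
- **Readers can rebuild the interval from the count and the percentage.** Largely true for success rates. It does not hold for survival with censored patients, where the interval cannot be recovered from a single percentage.
- **The public text is a synopsis.** It mentions eligibility criteria and radiographic success without defining them, so a fuller internal plan may exist. Nothing in the supplied text points to one that contains an interval or a benchmark. This lowers confidence without answering the point.

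A reader might go further and infer that any result at all could be declared a confirmation, or that 100 patients are too few. The documents support neither. They contain no rule for claiming confirmation, permissive or otherwise, and they leave interval estimates unmentioned without excluding them. Adequacy of 100 cannot be judged without a goal.

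**Conclusion.** The point holds in a limited form. As written, the analysis supports an estimate of success, survival and event rates. It does not support the statement that safety and performance have been confirmed, because there is no study-level benchmark, judging visit or interval.

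The uncertainty left unreported is material. A 90% success rate in 100 patients has a 95% interval nearly 13 percentage points wide (95.1 − 82.4 = 12.7), and with 70 evaluable it is about 15 (95.9 − 80.5 = 15.4). A 0% fracture rate in 100 leaves rates up to 3.6% open. These figures rest on assumed counts, an assumed 70 evaluable patients and, for survival, complete follow-up.

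The data remain usable and the defect is cheap to remove, so this should be changed but does not invalidate the study. Confidence is medium, because only synopsis-level text is available.

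**What to change.** 1. In the General Statistical Method, report each success rate, and the squeaking and ceramic fracture rates, with an exact or Wilson 95% confidence interval.
2. Report Kaplan-Meier implant survival at 10 years with a log-log 95% confidence interval and the number still at risk.
3. In the Objectives, replace *confirm* with *estimate*. State the expected precision for 100 patients and for the number expected at 10 years.
4. Keep *confirm* only if a reference value, a judging visit and a lower-limit rule are pre-specified, and the chance that 100 patients meet the rule is stated. This option is more than a wording change: under the assumed 90% reference, the chance of meeting the rule is 44% at a true rate of 95%, and 31% with 70 evaluable.

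Items 1 to 3 need no extra patients, visits or data. The price is a more modest claim.

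### Does the word 'modified' put the success cut of 80 on a Harris Hip score that the study does not collect?

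*Combined protocol and SAP*

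**What the plan says.** All the relevant text is in the synopsis. The Objectives row states: "Pain and functional performance will be measured using the Harris Hip Score". The Clinical Assessments row lists what is collected: "Evaluations will be made using the Harris Hip Score, Oxford Hip Score, EQ-5D and radiographic evaluation". Neither row mentions a modified version.

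The General Statistical Method section rests the efficacy assessment on pain and function, and then sets two cuts. Success is worded as "Clinical success will be defined as a modified Harris Hip score of > 80", together with a pain rating of mild or none, and the other side as "a failure will be defined as a modified Harris Hip score < 80". The next sentence makes any hip with a removed or planned-for-removal component a failure; such a hip "was considered a failure regardless of the Harris Hip score". The adjective is absent there.

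On reporting, the section says that "primary summary results will be presented in tables which will contain the number and percentage of patients classified as a clinical success". No outcome is formally named primary, and the Objectives open without ranking: "The objectives of this study are to obtain survival and outcomes data on the Alloclassic® Variall® Cup".

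**The concern.** The adjective appears in exactly the two places where a number separates success from failure, and nowhere in the text that says what is measured. Its items, maximum, scaling and derivation are not given. If the modified score were a different scale, a patient could exceed 80 on one version and not on the other. Sites would complete one form while the analyst needed another.

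The success percentage feeds the main summary tables. With no comparator group, no second arm scored in the same way would cancel a scale error. With 100 patients, if all are evaluable, each patient who changes class moves the reported percentage by 1/100, or 1 percentage point.

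**Working it through.** The plan states no figure that depends on the version of the score, so there is nothing to reproduce. The check is a comparison of every mention of the score, followed by a test of whether a size can be attached.

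**Step 1: the five mentions.**

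| Place in the synopsis | Name used | Role |
|---|---|---|
| Objectives | Harris Hip Score | how pain and function are measured |
| Clinical Assessments | Harris Hip Score | what is collected |
| General Statistical Method, success | modified Harris Hip score | cut above 80 |
| General Statistical Method, failure | modified Harris Hip score | cut below 80 |
| General Statistical Method, removal | Harris Hip score | score overridden by removal |

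Three mentions are unmodified and two are modified.

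**Step 2: do the names denote one score or two?** The removal sentence exists to override the classification just defined. It does so only if the score it names is the one the cuts use. Read as a different instrument, the sentence would override a score that had played no part in the rule. The efficacy sentence also bases the assessment on pain and function, and the Objectives say the Harris Hip Score measures both. The success rule asks for a pain rating within the score, which fits an instrument that covers pain.

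**Step 3: the three possible readings.**

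1. *Loose naming for the collected score.* The cut applies to the score as collected. Nothing changes.
2. *A version computed from the collected items.* The data are on the form, and the analyst specifies the derivation. Nothing extra is collected.
3. *A separate instrument that is not collected.* This is the only reading under which the rule could not be carried out. No sentence supports it, and the removal sentence speaks against it.

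**Step 4: can a size be given?** Only by inventing a scale. Assume, for illustration, a 100-point full score and a modified version that drops *k* points; the documents give neither the 100 nor any *k*.

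- Without rescaling, a cut of 80 as a share of the new maximum is 80/(100 − *k*):
  - *k* = 0: 80/100 = 80.0%
  - *k* = 5: 80/95 = 84.2%
  - *k* = 10: 80/90 = 88.9%
- With rescaling to 100, the raw points needed are 0.8 × (100 − *k*), which gives 80, 76 and 72. As a share of the maximum, 72/90 = 80.0%, so the relative cut does not move.

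The assumed change is therefore between 0 and 8.9 percentage points of the maximum, depending wholly on an assumed *k* and on whether the score is rescaled. Turning that into a change in the success rate would need the expected distribution of scores near 80, which the documents do not give. No number of reclassified patients can be derived, and that number may be zero.

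**The case for a change.** The best argument for acting is that some correction follows on every reading. If the two names mean the same thing, the adjective is an error to delete; if they do not, the cut lacks a stated scale. The edit costs no patients, visits or, probably, data. Settling the version before success rates are tabulated would also rule out choosing it after the results are seen. Follow-up runs to 10 years at several centers, so an unwritten scoring rule could be applied differently from one analysis to the next.

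Part of this stands. The adjective is undefined in the available text, the naming is inconsistent, and tidying it would do no harm. What does not stand is the step to a faulty plan. No wrong result has been shown to come from following the plan as written. The split between what sites collect and what the analyst needs disappears if the score can be derived from the same form. No comparison with published success rates is planned in the text, so a mismatch of scales with outside figures is not something the plan would produce. Selective choice of version has limited force where results are counts and percentages and no test or performance goal is attached to the success rate.

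The available text is also a synopsis. It refers to eligibility criteria that it does not list, so some detail sits elsewhere. Whether the scoring definition does too cannot be confirmed from what is here, and the conclusion does not depend on it.

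**Conclusion.** The wording is inconsistent, but the success rule is not shown to rest on an uncollected instrument. The point comes down to one undefined adjective, used twice beside three unmodified mentions of what reads as the same score. An analyst has to fix the scoring algorithm before any table can be programmed, and would ordinarily state the version with the result. That fills the gap without altering design, data collection or method.

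The size is not computable from the documents. Under the illustrative scale it runs from no shift in the relative cut to 8.9 percentage points of the maximum, with no basis for converting either into a success rate.

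The conclusion rests on two things: that the modified score is either the collected score or obtainable from its items, as the adjoining sentence suggests; and that the success rate stays descriptive, as the text now has it. It would need another look if the form lacked items the modified version requires, or if a performance goal were set on the success rate. It covers the naming of the score only. Other features of the same rule, such as how a score of exactly 80 is classed, are separate questions.

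### Do the success and failure rules leave some patients unclassified in a way that harms the efficacy result?

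*Combined protocol and SAP*

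**What the plan says.** The rules are in the synopsis, Statistical analysis, General Statistical Method. Efficacy "will be determined using the overall pain score and functional performance". Three rules follow:

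- Success: "Clinical success will be defined as a modified Harris Hip score of > 80 that included a rating of 'mild', or 'no pain'".
- Failure by score: "a failure will be defined as a modified Harris Hip score < 80".
- Failure by removal: a hip with a component taken out, or a removal planned, "was considered a failure regardless of the Harris Hip score".

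The summary tables are to contain "the number and percentage of patients classified as a clinical success for the treatment group". No failure percentage is named. The synopsis gives the enrolment as 100 patients, describes the design as non-controlled, and lists no comparator. It states no target success rate.

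**The concern.** Failure has its own definition and is not simply the absence of success, so the two rules need not cover every patient. Both inequalities are strict, which leaves a score of exactly 80 unassigned. The failure rule also has no pain condition, although the success rule has one and efficacy is to be judged partly on pain. A hip scoring above 80 with more than mild pain therefore fails the success rule without meeting the failure rule.

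This is the stated efficacy outcome, reported over ten years of follow-up. If unclassified patients were dropped from the denominator, or if success were reported as 100% minus failures, the result could look better than the success rule allows. Different programmers could also place these patients differently from one report to the next.

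**Working it through.** **Inputs.** The three rules and the planned table content come from General Statistical Method; N = 100 comes from Number of Subjects. The documents give no success counts, no number scoring exactly 80 and no item weights for the modified score. Those values are assumptions below. The plan has no success figure to reproduce.

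**Step 1: is the classification complete?** Cross three score bands (below 80, exactly 80, above 80) with two pain levels (none or mild; worse) and two removal states (no; done or planned). This gives 3 × 2 × 2 = 12 cells.

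| Reading | Success | Failure | Neither |
|---|---|---|---|
| As printed | 1 | 8 | 3 |
| Success meant as ≥ 80 | 2 | 8 | 2 |
| Failure meant as ≤ 80 | 1 | 10 | 1 |

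No cell falls in both classes, and all 6 removal cells are failures under every reading. As printed, the three unassigned cells, all without removal, are: exactly 80 with no or mild pain; exactly 80 with worse pain; above 80 with worse pain. The last stays unassigned under all three readings.

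**Step 2: can the pain gap contain anyone?** Assume a maximum of 100 points, and let d be the points lost for pain worse than mild. The highest score such a hip can reach is 100 − d.

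- d = 19: 100 − 19 = 81, so the gap can occur.
- d = 20: 100 − 20 = 80, so no such hip exceeds 80, though one could sit exactly on 80.
- d = 21: 100 − 21 = 79, so every such hip is a failure by score.

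The documents do not give d, so this gap may be empty.

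**Step 3: effect on the reported rate.** Let S be successes, k unclassified patients and F = N − S − k failures, with N = 100, all assessed, and S = 85 assumed.

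- Planned rate: S/N
- Rate on classified patients only: S/(S + F) = S/(N − k)
- 100% minus failures: (N − F)/N = (S + k)/N

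| k | S/N | S/(N − k) | (S + k)/N |
|---|---|---|---|
| 0 | 85.0% | 85.0% | 85.0% |
| 1 | 85.0% | 85/99 = 85.9% | 86.0% |
| 2 | 85.0% | 85/98 = 86.7% | 87.0% |
| 5 | 85.0% | 85/95 = 89.5% | 90.0% |
| 10 | 85.0% | 85/90 = 94.4% | 95.0% |

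With k = 1, the middle rate is 80/99 = 80.8% for S = 80 and 90/99 = 90.9% for S = 90, so the shift is about 0.8 to 0.9 points.

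**Step 4: which side of the cut is 80 on?** If 80 was meant as a failure, S does not change. If it was meant as a success, each patient at 80 with no or mild pain adds 1/100 = 1.0 point to the success rate, so the printed rule understates success. For that patient, 100% minus failures would already be right. An unclassified patient is therefore not automatically a missed failure.

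**The case for a change.** The strongest case for a change is that this is the headline efficacy measure, that an incomplete rule leaves the choice to whoever programs each report, and that two or three sentences would close it with no new data. A lost ≥ or ≤ sign does not dispose of the point either: it would explain the gap at exactly 80 but not the missing pain condition in the failure rule. The tables are said to contain successes, which does not exclude a failure column.

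The reading of the text stands: the two rules are not exhaustive as printed. The harm is not shown. Both unclassified groups plainly miss the success rule, so an analyst producing the planned table counts them as non-successes without needing the failure sentence. The rates that move in Step 3 are not named in the plan. With one group and no target rate, a point or so either way decides nothing.

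A wider rewrite could also do damage. Suppose the denominator were redefined as assessed cases plus removals. With an assumed 85 successes and 10 patients unscored without removal, the rate would go from 85/100 = 85.0% to 85/90 = 94.4%. That is as large a favourable shift as any in the table, and it comes from missing scores, which are a separate matter.

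**Conclusion.** No change to the plan is needed. The failure sentence is loosely drafted, but the planned result rests on the success rule, which is complete. Taken over all patients in the treatment group, the success percentage moves by 0 points whatever the number of unclassified patients, provided that 80 is not a success, as printed. If 80 was meant as a success, the printed percentage is too low by 1.0 point per patient at exactly 80 with no or mild pain, which errs against the device. The pain gap may contain nobody.

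This conclusion assumes that the denominator is all patients in the group, which is the natural reading of the table description, and that no failure-based rate is reported as the efficacy result. Should an analyst add a failure column, the sensible convention is to treat every assessed case that is not a success as a failure, together with all removals done or planned. Where a score of 80 belongs is a clerical question the sponsor can answer when programming the tables.
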